#### 8.1.2 The Second Stage Screening (-42 ≤ Day < 0)

This visit is scheduled between the first stage screening visit and visit 1 and includes:

- Record of AEs and SAEs
- Record of the use or change of any concomitant medications
- Physical examination
- Vital signs, including temperature, respiratory rate, heart rate, blood pressure, and body weight
- 18F-AV-45 PET imaging

#### 8.1.3 Visit 1 (Week 0, Day 0 / baseline)

This visit (V1) should be scheduled within 6 weeks after S1 and includes:

- Verification of Inclusion/Exclusion criteria and check for eligibility
- IVRS/IWRS call for randomization
- Survey instruments
  - ADAS-Cog
  - ADCS-ADL
  - NPI
- Record of AEs and SAEs
- Record of the use or change of any concomitant medications
- Physical examination
- Vital signs, including temperature, respiratory rate, heart rate, blood pressure, and body weight
- Blood collection for: (before the UB-311/Placebo injection)

- Anti-A $\beta$  antibodies
- TNF- $\alpha$ , IL-6, and IL-8
- Clinical chemistry (glucose AC, AST, ALT, bilirubin, sodium, total protein, BUN, creatinine, potassium, and albumin)
- Hematology (complete blood count including differential cell count and absolute neutrophil count)
- APO-E genotyping
- Injecting study drug
- Injection site assessments, vital signs (except body weight), and neurology examination of physical examination 30-60 minutes after injection

#### 8.1.4 Visit 2 (Week 4, Day 28)

This visit (V2) should be scheduled 4 weeks  $\pm$  3 days after V1 and includes:

- Record of AE and SAE
- Record of the use or change of any concomitant medications
- Physical examination
- Vital signs, including temperature, respiratory rate, heart rate, blood pressure, and body weight
- Blood sampling for: (before the UB-311/Placebo injection)
  - Anti-A $\beta$  antibodies
  - CRP, ESR, TNF- $\alpha$ , IL-6, and IL-8
  - Clinical chemistry (glucose AC, AST, ALT, bilirubin, sodium, total protein, BUN, creatinine, potassium, and albumin)
  - Hematology (complete blood count including differential cell count and absolute neutrophil count)
- Injecting study drug
- Injection site assessment, vital signs (except body weight), and neurology examination of physical examination 30-60 minutes after injection

#### 8.1.5 Visit 3 (Week 12, Day 84)

This visit (V3) should be scheduled 12 weeks  $\pm$  3 days after V1 and includes:

- Structural MRI scanning (should be scheduled < 7 days before the injection of study drug)
- Record of AEs and SAEs
- Record of the use or change of any concomitant medications
- Physical examination

- Vital signs, including temperature, respiratory rate, heart rate, blood pressure, and body weight
- Blood collection for: (before the UB-311/Placebo injection)
  - Anti-A $\beta$  antibodies
  - Clinical chemistry (glucose AC, AST, ALT, bilirubin, sodium, total protein, BUN, creatinine, potassium, and albumin)
  - Hematology (complete blood count including differential cell count and absolute neutrophil count)
- Injecting study drug
- Injection site assessment, vital signs (except body weight), and neurology examination of physical examination 30-60 minutes after injection

#### 8.1.6 Visit 4 (Week 16, Day 112)

This visit (V4) should be scheduled 16 weeks  $\pm$  3 days after V1 and includes:

- Record of AEs and SAEs
- Record of the use or change of any concomitant medications
- Physical examination
- Vital signs, including temperature, respiratory rate, heart rate, blood pressure, and body weight
- Blood collection for:
  - Anti-A $\beta$  antibodies
  - CRP and ESR
  - Clinical chemistry (glucose AC, AST, ALT, bilirubin, sodium, total protein, BUN, creatinine, potassium, and albumin)
  - Hematology (complete blood count including differential cell count and absolute neutrophil count)

#### 8.1.7 Visit 5 (Week 24, Day 168)

This visit (V5) should be scheduled 24 weeks  $\pm$  3 days after V1 and includes:

- Structural MRI scanning (should be scheduled < 7 days before the injection of study drug)
- Survey instruments
  - MMSE
  - CDR-SB
- Record of AEs and SAEs
- Record of the use or change of any concomitant medications

- Physical examination
- Vital signs, including temperature, respiratory rate, heart rate, blood pressure, and body weight
- Blood collection for: (before the UB-311/Placebo injection)
  - Anti-A $\beta$  antibodies
  - Clinical chemistry (glucose AC, AST, ALT, bilirubin, sodium, total protein, BUN, creatinine, potassium, and albumin)
  - Hematology (complete blood count including differential cell count and absolute neutrophil count)
- Injecting study drug
- Injection site assessment, vital signs (except body weight), and neurology examination of physical examination 30-60 minutes after injection

#### 8.1.8 Visit 6 (Week 28, Day 196)

This visit (V6) should be scheduled 28 weeks  $\pm$  3 days after V1 and includes:

- Survey instruments
  - ADAS-Cog
  - ADCS-ADL
  - NPI
- Record of AEs and SAEs
- Record of the use or change of any concomitant medications
- Physical examination
- Vital signs, including temperature, respiratory rate, heart rate, blood pressure, and body weight
- Blood sampling for:
  - Anti-A $\beta$  antibodies
  - CRP and ESR
  - Clinical chemistry (glucose AC, AST, ALT, bilirubin, sodium, total protein, BUN, creatinine, potassium, and albumin)
  - Hematology (complete blood count including differential cell count and absolute neutrophil count)

#### 8.1.9 Visit 7 (Week 36, Day 252)

This visit (V7) should be scheduled 36 weeks  $\pm$  3 days after V1 and includes:

- Structural MRI scanning (should be scheduled < 7 days before the injection of study drug)

- Record of AEs and SAEs
- Record of the use or change of any concomitant medications
- Physical examination
- Vital signs, including temperature, respiratory rate, heart rate, blood pressure, and body weight
- Blood sampling for: (before the UB-311/Placebo injection)
  - Anti-A $\beta$  antibodies
  - Clinical chemistry (glucose AC, AST, ALT, bilirubin, sodium, total protein, BUN, creatinine, potassium, and albumin)
  - Hematology (complete blood count including differential cell count and absolute neutrophil count)
- Injecting study drug
- Injection site assessment, vital signs (except body weight), and neurology examination of physical examination 30-60 minutes after injection

#### 8.1.10 Visit 8 (Week 40, Day 280)

This visit (V8) should be scheduled 40 weeks  $\pm$  3 days after V1 and includes:

- Record of AEs and SAEs
- Record of the use or change of any concomitant medications
- Physical examination
- Vital signs, including temperature, respiratory rate, heart rate, blood pressure, and body weight
- Blood sampling for:
  - Anti-A $\beta$  antibodies
  - CRP and ESR
  - Clinical chemistry (glucose AC, AST, ALT, bilirubin, sodium, total protein, BUN, creatinine, potassium, and albumin)
  - Hematology (complete blood count including differential cell count and absolute neutrophil count)

#### 8.1.11 Visit 9 (Week 48, Day 336)

This visit (V9) should be scheduled 48 weeks  $\pm$  3 days after V1 and includes:

- Structural MRI scanning (should be scheduled < 7 days before the injection of study drug)
- Survey instruments
  - MMSE

- CDR-SB
- Record of AEs and SAEs
- Record of the use or change of any concomitant medications
- Physical examination
- Vital signs, including temperature, respiratory rate, heart rate, blood pressure, and body weight
- Blood sampling for: (before the UB-311/Placebo injection)
  - Anti-A $\beta$  antibodies
  - Clinical chemistry (glucose AC, AST, ALT, bilirubin, sodium, total protein, BUN, creatinine, potassium, and albumin)
  - Hematology (complete blood count including differential cell count and absolute neutrophil count)
- Injecting study drug
- Injection site assessment, vital signs (except body weight), and neurology examination of physical examination 30-60 minutes after injection

#### 8.1.12 Visit 10 (Week 52, Day 364)

This visit (V10) should be scheduled 52 weeks  $\pm$  3 days after V1 and includes:

- 18F-AV-45 PET scanning (a time frame of  $\pm$  7 days is acceptable)
- 12-lead ECG
- Survey instruments
  - ADAS-Cog
  - ADCS-ADL
  - NPI
- Record of AEs and SAEs
- Record of the use or change of any concomitant medications
- Physical examination
- Vital signs, including temperature, respiratory rate, heart rate, blood pressure, and body weight
- Blood collection for:
  - Anti-A $\beta$  antibodies
  - CRP and ESR
  - Clinical chemistry (glucose AC, AST, ALT, bilirubin, sodium, total protein, BUN, creatinine, potassium, and albumin)

- Hematology (complete blood count including differential cell count and absolute neutrophil count)

#### 8.1.13 Visit 11 (Week 60, Day 420)

This visit (V11) should be scheduled 60 weeks  $\pm$  3 days after V1 and includes:

- Structural MRI scanning (should be scheduled < 7 days before the injection of study drug)
- Record of AEs and SAEs
- Record of the use or change of any concomitant medications
- Physical examination
- Vital signs, including temperature, respiratory rate, heart rate, blood pressure, and body weight
- Blood sampling for: (before the UB-311/Placebo injection)
  - Anti-A $\beta$  antibodies
  - Clinical chemistry (glucose AC, AST, ALT, bilirubin, sodium, total protein, BUN, creatinine, potassium, and albumin)
  - Hematology (complete blood count including differential cell count and absolute neutrophil count)
- Injecting study drug
- Injection site assessment, vital signs (except body weight), and neurology examination of physical examination 30-60 minutes after injection

#### 8.1.14 Visit 12 (Week 64, Day 448)

This visit (V12) should be scheduled 64 weeks  $\pm$  3 days after V1 and includes:

- Record of AEs and SAEs
- Record of the use or change of any concomitant medications
- Physical examination
- Vital signs, including temperature, respiratory rate, heart rate, blood pressure, and body weight
- Blood sampling for:
  - Anti-A $\beta$  antibodies
  - CRP, ESR, TNF- $\alpha$ , IL-6, and IL-8
  - Clinical chemistry (glucose AC, AST, ALT, bilirubin, sodium, total protein, BUN, creatinine, potassium, and albumin)
  - Hematology (complete blood count including differential cell count and absolute neutrophil count)

### 8.1.15 Visit 13 (Week 78, Day 546)

This visit (V13) should be scheduled 78 weeks  $\pm$  7 days after V1 and includes:

- Structural MRI scanning
- 18F-AV-45 PET scanning
- 12-lead ECG
- Survey instruments
  - MMSE
  - CDR-SB
  - ADAS-Cog
  - ADCS-ADL
  - NPI
- Record of AEs and SAEs
- Record of the use or change of any concomitant medications
- Physical examination
- Vital signs, including temperature, respiratory rate, heart rate, blood pressure, and body weight
- Blood collection for:
  - Anti-A $\beta$  antibodies
  - Clinical chemistry (glucose AC, AST, ALT, bilirubin, sodium, total protein, BUN, creatinine, potassium, and albumin)
  - Hematology (complete blood count including differential cell count and absolute neutrophil count)

## 8.2 Events and Time Schedule

Visit	S1 	S2 	V1	V2	V3	V4	V5	V6	V7	V8	V9	V10	V11	V12	V13
Week	-6	~ 0	0/BL	4	12	16	24	28	36	40	48	52	60	64	78/ET
Day	-42	~ 0	0	28±3	84±3	112±3	168±3	196±3	252±3	280±3	336±3	364±3	420±3	448±3	546±7
ICF, medical history & concomitant disease, demographics	X														
Incl./excl. criteria	X	X	X												
Randomization			X												
ECG	X											X			X
MRI 	X				X		X		X		X		X		X
18F-AV-45 PET 		X										X			X
APO-E genotyping			X												
NINCDS-ADRDA, HIS, GDS-SF, ECOG	X														
MMSE, CDR  /CDR-SB	X						X				X				X
ADAS-Cog, ADCS-ADL & NPI			X					X				X			X
AE/SAE	X	X	X	X	X	X	X	X	X	X	X	X	X	X	X
Previous and concomitant medicines	X	X	X	X	X	X	X	X	X	X	X	X	X	X	X
PE  /vital signs	X	X	X	X	X	X	X	X	X	X	X	X	X	X	X
HIV, HCV, HBsAg test	X														
Clinical chemistry  & hematology 	X		X*	X*	X*	X	X*	X	X*	X	X*	X	X*	X	X
Inflammatory 	X		X	X*		X		X		X		X		X	
PT & aPTT	X														
Serum pregnancy test 	X														
Anti-Aβ Ab level in serum			X*	X*	X*	X	X*	X	X*	X	X*	X	X*	X	X
Vaccination/injection site assessment/ Neurology/vital signs 			X	X	X		X		X		X		X		
vMRI	X										X				X
fMRI	X										X				X
Plasma Aβ 40/42 levels			X*	X*	X*	X	X*	X	X*	X	X*	X	X*	X	X
Anti-Aβ 1-42 monomer & oligomer Antibodies			X*	X*	X*	X	X*	X	X*	X	X*	X	X*	X	X
CSF tau & Aβ 40/42 levels (optional)			X*									X			X

BL=baseline; ET=early termination; vMRI=volumetric magnetic resonance imaging; fMRI=functional magnetic resonance imaging

- For V3 (Week 12), V5 (Week 24), V7 (Week 36), V9 (Week 48), and V11 (Week 60), MRI should be scheduled <7 days before the injection of study drug. For V13, a time frame of ± 7 days is acceptable.
- For V13, a time frame of ± 7 days is acceptable.
- CDR: for S1 only
- Including height (for S1 only)
- Clinical chemistry: HbA1c (for S1 only), glucose AC, AST, ALT, bilirubin, sodium, total protein, BUN, creatinine, potassium, and albumin at S1 and every visit throughout the study (V1 to V13); Hematology: complete blood count including differential

- cell count and ANC at S1 and every visit throughout the study (V1 to V13).
6. Inflammatory parameters: RF and ANA (for S1 only); CRP and ESR: for S1, V2 (Week 4), V4 (Week 16), V6 (Week 28), V8 (Week 40), V10 (Week 52), and V12 (Week 64); TNF- $\alpha$ , IL-6, and IL-8: for V1, V2 (Week 4), and V12 (Week 64).
  7. For females with childbearing potential.
  8. 30-60 minutes after injection. Vital sign: not need to measure body weight.
  9. Criteria are screened at S1. Subjects meeting inclusion criteria 1 to 14 and none of the exclusion criteria are eligible for the S2. S1 and S2 should be done within 6 weeks before V1.
- \* Blood or CSF specimens should be drawn before the UB-311/Placebo injection.

### 8.3 Blood Sample Collection

For visits that UB-311 or placebo is scheduled to be administrated (V1, V2, V3, V5, V7, V9, and V11), blood samples will be collected before the treatment.

Visit	S1	V1	V2	V3	V4	V5	V6	V7	V8	V9	V10	V11	V12	V13
Week	-6~0	0/BL	4	12	16	24	28	36	40	48	52	60	64	78/ET
Day	-42~0	0	28±3	84±3	112±3	168±3	196±3	252±3	280±3	336±3	364±3	420±3	448±3	546±7
Vaccination		X	X	X		X		X		X		X		
Clotted Blood														
HIV, HCV, HBsAg, RF, ANA and serum pregnancy test 	5 mL													
Clinical chemistry  except HbA1c and Glucose AC, CRP 	5 mL	5 mL	5 mL	5 mL	5 mL	5 mL	5 mL	5 mL	5 mL	5 mL	5 mL	5 mL	5 mL	5 mL
TNF- $\alpha$ , IL-6, and IL-8		3.5 ml	3.5 ml										3.5 ml	
Anti-A $\beta$ , and anti- A $\beta$ 1-42 monomer and oligomer 		2 mL	2 mL	2 mL	2 mL	2 mL	2 mL	2 mL	2 mL	2 mL	2 mL	2 mL	2 mL	2 mL
EDTA Blood														
Hematology  and HbA1c 	3 mL	3 mL	3 mL	3 mL	3 mL	3 mL	3 mL	3 mL	3 mL	3 mL	3 mL	3 mL	3 mL	3 mL
ESR	3 mL		3 mL		3 mL		3 mL		3 mL		3 mL		3 mL	
APO-E genotyping		3 mL												
A $\beta$ 40/42 		2 mL	2 mL	2 mL	2 mL	2 mL	2 mL	2 mL	2 mL	2 mL	2 mL	2 mL	2 mL	2 mL
NaF Blood														
Glucose AC	2 ml	2 ml	2 ml	2 ml	2 ml	2 ml	2 ml	2 ml	2 ml	2 ml	2 ml	2 ml	2 ml	2 ml
Citrated Blood														
PT, aPTT	2.7 mL													

BL=baseline; ET=early termination

Note: In the case of testing failure, residual samples of the subject from other tests may be used for retesting.

1. Only for females with childbearing potential;
2. Clinical chemistry: AST, ALT, bilirubin, sodium, total protein, BUN, creatinine, potassium, and albumin at S1 and every visit throughout the study (V1 to V13);
3. CRP: for screening, V2 (Week 4), V4 (Week 16), V6 (Week 28), V8 (Week 40), V10 (Week 52), and V12 (Week 64);
4. For research study;
5. Hematology: complete blood count including differential cell count and ANC at S1 and every visit throughout the study (V1 to V13);
6. HbA1c: for screening only.

## 9 STATISTICS

The material of this section is the basis for the Statistical Analysis Plan (SAP) for the study. The SAP may be revised during the study to accommodate Clinical Trial Protocol amendments and to make changes to adapt to unexpected issues in study execution and data that may affect planned analyses.

### 9.1 Determination of Sample Size

This early phase clinical trial is exploratory in nature; hence, the sample size is determined to assess the primary objective of safety, tolerability, and immunogenicity of UB-311. The total of 45 subjects is planned to be enrolled, 15 per arms. For each UB-311-treated arm, 15 subjects are thought to be sufficient to detect an adverse event with an incidence of 7%. Furthermore, 30 subjects receiving UB-311 are anticipated to be able to detect an adverse event with an incidence of 4%.

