
STUDY POPULATION
 
Total expected number of subjects
 
Inclusion criteria
	
Approximately 45 subjects will be enrolled to receive study treatment, approximately 15 subjects per treatment arm.
 
Subjects may be included in the clinical trial only if they meet all of the following criteria:
 
 
1. Male or female aged between 60-90 years old;
 
2. Probable Alzheimer’s disease based on the National Institute of Neurological and Communicative Disorders and Stroke and the Alzheimer’s Disease and Related Disorders Association (NINCDS-ADRDA) criteria and National Institute on Aging–Alzheimer’s Association (NIA-AA) guidelines;
 
3. Mini-Mental State Examination (MMSE) scores between 20 and 26 (inclusive);
 
4. Clinical dementia rating (CDR) scores of 0.5 or 1;
 
5. At least 6 years of education or sufficient work history (to exclude mental retardation);
 
6. Visual and auditory acuity adequate for neuropsychological testing;
 
7. Stable doses of permitted medications for 3 months before screening, such as acetyl cholinesterase (AChE) inhibitors, N-methyl-D-aspartate (NMDA) receptor antagonist, ergot alkaloids or their derivatives for cognitive enhancement;
 
8. Hachinski ischemic score (HIS) <math>\leq 4</math> (original score);
 
9. Geriatric Depression Scale-Short Form (GDS-SF) <math>< 6</math>;
 
10. Eastern Cooperative Oncology Group (ECOG) performance status 0-2;
 
11. Female must either be post-menopausal (no menstrual period for <math>> 1</math> year), surgically sterilized or agree to avoid becoming pregnant during the entire period of this study; while sexually active fertile male must agree to use effective birth control methods throughout the study duration, if their sexual partner(s) are women of childbearing potential;
 
12. With a caregiver who has frequent contact with the subject (e.g. an average of 10 hours per week or more) and agrees to sign the informed consent form (ICF), to perform study-related AD scales and to accompany or delegate a companion with the subject to all visits. A companion needs not to be a family member (with kinship);
 
13. Both patient and his/her caregiver should sign the written
 

---	--

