The pathology of AD is characterized by a progressive loss of neurons and synapses with the presence of large numbers of extracellular amyloid plaques and intracellular neurofibrillary tangles. Although symptomatic therapies are available, there is still no proven treatment that can address a variety of neurobehavioral disturbances and reverse progression of AD. Increased amyloid beta (A $\beta$ ) production or reduced A $\beta$  catabolism has been implicated in the pathogenesis of AD. Therapeutic targets have focused on reducing A $\beta$  deposition in brain and evidence shows that antibodies targeting A $\beta$  can improve symptoms of AD. Results from successful immunotherapy with aggregated A $\beta_{1-42}$  in transgenic mice overexpressing A $\beta_{1-42}$  peptide led to the development of the first human active immunization trial with synthetic aggregated A $\beta_{1-42}$  peptide AN1792 in combination with QS-21 adjuvant. Analysis of AN1792-treated subjects showed that about 20% developed robust antibody response but available data on efficacy showed no significant effects on exploratory measures of cognition (Alzheimer's Disease Assessment Scale – Cognitive subscale [ADAS-Cog]) or disability (Disability Assessment for Dementia [DAD], Clinical Dementia Rating [CDR], Mini Mental State Examination [MMSE]). However, significant improvements were observed in a nine component neuropsychological test battery (NTB), indicating less worsening of performance in anti-A $\beta$  antibody responders. Improvements in memory were associated with increased antibody response and decreased tau in the cerebrospinal fluid in a small subset of patients. The AN1792-treated subjects were examined by magnetic resonance imaging (MRI) for cerebral volume changes; greater decrease of brain volume was noted without cognitive decline in antibody responders. Postmortem observations from three patients showed brain regions that were devoid of amyloid plaques. Unfortunately, the trial was halted after reports of acute meningoencephalitis in 18 of 300 patients treated with AN1792.

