### 5.2 Dosing Regimens and Rationale

Eligible subjects are randomly assigned in 1:1:1 ratio to one of the following treatments:

- Arm 1: UB-311 for a total of 7 intramuscular (IM) injections at Weeks 0, 4, 12, 24, 36, 48, and 60.
- Arm 2: UB-311 for a total of 5 IM injections at Weeks 0, 4, 12, 36, and 60. In order to maintain the blindness, subjects assigned to arm 2 will receive 2 IM injections of placebo at Weeks 24 and 48.
- Arm 3: placebo for a total of 7 IM injections at Weeks 0, 4, 12, 24, 36, 48, and 60.

Injections will be given on alternate arms or at different sites, which will be recorded.

The 300 µg of UB-311 in 0.5 mL sterile aqueous solution is the maximal concentration feasible in the current intramuscular injection formulation containing CpG-ODN and Adjuvphos. Therefore, the dose escalation in the Phase IIa study will be based on the cumulative doses according to various treatment schedules instead of different amount of UB-311 per injection.

A total of three injections of UB-311 at Weeks 0, 4, and 12 with a cumulative dose of 900 µg were evaluated in the Phase I clinical trial that showed acceptable safety, tolerability, immunogenicity, and positive clinical outcome in mild to moderate AD patients over a one-year period. In the Phase IIa study, the dose will be escalated based on increased number of injections than the Phase I study. Subjects assigned to Arm 1 will receive 7 injections of UB-311, 300 µg each at Weeks 0, 4, 12, 24, 36, 48, and 60 with a cumulative dose of 2,100 µg. Subjects assigned to Arm 2 will receive 5 injections of UB-311, 300 µg each at Weeks 0, 4, 12, 36, and 60 with a cumulative dose of 1,500 µg.

The Phase I study showed that three priming doses at Weeks 0, 4, and 12 successfully established sufficient immunogenicity against Aβ, thus the priming schedule was adopted for the current study. Additional doses for Arm 1 and Arm 2 at the frequency of 3 and 6 months, respectively, are intended to assess the requirement for maintaining elicited antibody levels. Furthermore, the dosing regimen of Arm 1 represents the most frequent injection schedule, allowing evaluation of safety and efficacy of the strongest antibody response.

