## **7.10 Risk Management**

Postvaccination meningoencephalitis was reported in over 6% of patients treated with AN1792 for AD. Based on the experiences of AN1792 clinical trials, the following measures are used to manage potential risks:

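### The sample-size rationale says 15 and 30 subjects can detect 7% and 4% adverse events, but the chance of seeing even one case is only 66.3% and 70.6%

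*Protocol*

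**What the plan says.** Protocol 9.1 calls the trial exploratory and states that "the sample size is determined to assess the primary objective of safety, tolerability, and immunogenicity of UB-311". The allocation follows: "The total of 45 subjects is planned to be enrolled, 15 per arms". The numerical support is two sentences. For a single UB-311 arm, "15 subjects are thought to be sufficient to detect an adverse event with an incidence of 7" percent. For the two UB-311 arms together, "30 subjects receiving UB-311 are anticipated to be able to detect an adverse event with an incidence of 4" percent.

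SAP 5.13 repeats both sentences. Protocol 7.10 item 2 repeats only the 30-subject one and lists it among the measures for managing risk. That section opens with the experience of an earlier amyloid vaccine: "Postvaccination meningoencephalitis was reported in over 6% of patients treated with AN1792".

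None of the three places says what counts as detecting an event, or gives a probability, a confidence level or a formula. SAP 5.13 adds a warning about limited power, but it covers only the SUVR, cognitive and functional endpoints, not adverse events.

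**The concern.** Safety is a primary objective, and these two sentences are the only quantitative support for the sample size. A reader on an ethics committee or the DSMB, or a reader of the study report, would take a statement that 15 subjects suffice to detect a 7% event to mean that the event would very probably be seen. Such a reader could then treat an arm with no cases as evidence against a rate of 7%. If the true chance of seeing no case is about one in three, that inference is unsafe, and the plan's wording invites it.

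**Working it through.** **Inputs.** Protocol 9.1 and SAP 5.13 give n = 15 with incidence 7% (one UB-311 arm), and n = 30 with incidence 4% (both UB-311 arms). Protocol 7.10 item 2 gives the second pair again. There is no stated probability to reproduce, so the check is what the stated pairs deliver.

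**Definition used.** Detection is taken as at least one case among n independent subjects with a common rate p, all fully observed. This is the most lenient reading; requiring two or more cases would lower every figure.

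**Chance of at least one case,** 1 − (1 − p)^n:

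- n = 15, p = 0.07: 1 − 0.93^15 = 0.663, so no case 33.7% of the time.
- n = 30, p = 0.04: 1 − 0.96^30 = 0.706, so no case 29.4% of the time.

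**Could rounding of the incidences explain it?** For 6.5% to 7.5% with n = 15 the chance runs from 63.5% to 68.9%. For 3.5% to 4.5% with n = 30 it runs from 65.7% to 74.9%. Neither range reaches 80%.

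**Which criterion would give 7% and 4%?**

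- At least one expected case: 15 × 0.07 = 1.05 and 30 × 0.04 = 1.20, while one percentage point lower gives 15 × 0.06 = 0.90 and 30 × 0.03 = 0.90. The stated figures are the smallest whole percentages that meet this criterion.
- A detection chance of two thirds: 1 − (1/3)^(1/15) = 7.1% and 1 − (1/3)^(1/30) = 3.6%, which round to 7% and 4%.

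Both fit, and neither is stated.

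**What usual levels would correspond to.** The incidence giving chance q is 1 − (1 − q)^(1/n). The n needed at incidence p is ln(1 − q)/ln(1 − p), rounded up.

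| Chance q | Incidence, n=15 | Incidence, n=30 | n needed at 7% | n needed at 4% |
|---|---|---|---|---|
| 80% | 10.2% | 5.2% | 23 | 40 |
| 90% | 14.2% | 7.4% | 32 | 57 |
| 95% | 18.1% | 9.5% | 42 | 74 |

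**Pooled figures for context.** With a common rate in the two UB-311 arms, a 7% event has a chance of 1 − 0.93^30 = 88.7% of appearing among the 30 subjects. For the earlier vaccine, Protocol section 1 reports that "the trial was halted after reports of acute meningoencephalitis in 18 of 300 patients treated with AN1792", which is 18/300 = 6.0%. At 6% the chance is 1 − 0.94^30 = 84.4%.

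**The case against.** The best defence is that nothing is miscalculated. No probability is stated, the wording is hedged, and the section calls the trial exploratory. Read as the smallest whole percentage with at least one expected case, both pairs are right. The 80%, 90% and 95% levels come from general practice, not from these documents. A 7% event that escapes one arm would usually show in the pooled 30.

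Most of this stands. There is no arithmetic error to correct, and an exploratory label justifies a small trial. It does not justify an affirmative statement of sufficiency that fails about one time in three on the most lenient meaning of the word. The expected-case reading is coherent, but a reader cannot recover it from the text. The pooled 88.7% does not answer the single-arm sentence, which is about 15 subjects.

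Three stronger readings are tempting and are not supported:

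- *The trial is undersized and needs 23 or 40 subjects.* The documents set no detection level, so these numbers only show the distance from common levels.
- *The trial is poorly placed to see the event that motivates Protocol 7.10.* At about 6%, 30 subjects have an 84.4% chance of showing a case.
- *Dropout makes the true figures materially lower.* The documents give no dropout rate. Protocol 4.1 continues randomization until the treated target is met, the safety population in 9.3.2 includes everyone dosed, and 4.4 asks for adverse-event follow-up of dropouts to Week 78.

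**Conclusion.** The statements are wrong as written, in a limited sense: they claim a detection property that the design does not have on the ordinary meaning of the word. The chance of at least one case is 66.3% for a 7% event in 15 subjects and 70.6% for a 4% event in 30, against a wording that signals sufficiency.

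The figures assume independent subjects, a common event rate and full observation. For n = 30 the common rate must hold across two regimens that differ in exposure. Arm 1 receives seven doses of the vaccine and Arm 2 receives "UB-311 for a total of 5 IM injections at Weeks 0, 4, 12, 36, and 60". Enrolment is also only approximate: "Approximately 45 subjects will be enrolled to receive study treatment, approximately 15 subjects per treatment arm".

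Severity is low. The stopping rule in Protocol 3.5 and the DSMB reviews in 7.9 work from observed safety data, the adverse-event analyses in 9.4.5 are descriptive, and none of them uses the 7% or 4% figure.

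**What to change.** Keep the sample size. In Protocol 9.1 and SAP 5.13 replace the two sentences with:

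> Assuming independent, fully observed subjects and a common event rate, 15 subjects per arm have a 66% chance of showing at least one case of an adverse event with a true incidence of 7%, and 30 pooled UB-311 subjects have a 71% chance at 4%. The incidence giving an 80% (95%) chance of at least one case is 10.2% (18.1%) for n=15 and 5.2% (9.5%) for n=30.

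In Protocol 7.10 item 2 use the 30-subject figures under the same assumptions. That item could also give the 84.4% chance at a true rate of 6%, which is the figure most relevant to the risk discussed there.

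The cost is a wording revision in three places across two controlled documents, and stated detectable incidences that look less favourable. Analyses, visits and decision rules stay as they are.
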